TGA/IVS	Transposition of the great arteries with intact ventricular septum
UV	Umbilical vein/venous
VSD	Ventricular septal defect
VTI	Velocity time integral

PROTOCOL SUMMARY

Title:	Transposition of the Great Arteries: Prenatal Anatomical and Hemodynamic Findings associated with Perinatal Outcomes
Short Title	Fetal TGA
Sponsor	[name]/The Hospital for Sick Children
Principal Investigator	[name]
Primary Objective	Determine the association between response to MH and neonatal outcome
Secondary Objectives	Determine the change of cerebral perfusion for acute MH
Study Population	Pregnant women with a fetal diagnosis of TGA
Study Design	Prospective pilot study
Sample Size	N = 50
End points	Fetal demise or neonatal death or neonatal discharge
Study Drug/ Intervention Description	Transient maternal oxygen administration during echocardiographic and MRI imaging

1. INTRODUCTION

In transposition of the great arteries (TGA), a condition that affects ~3/10,000 live-births, the aorta arises from the morphological right ventricle (RV) and the pulmonary artery from the left ventricle (LV) while the atrio-ventricular connections are concordant. The inverted great arterial arrangement can be anatomically corrected by an arterial switch operation (ASO) in early infancy with low perioperative mortality and excellent long-term results. In the prenatal circulation with the placenta as the sole source of fetal oxygenation, TGA is usually well tolerated. With the transition to the postnatal circulation at birth, the lesion may become immediately life-threatening as the RV pumps desaturated systemic venous blood back into the aorta while oxygenated blood from the lungs is forwarded by the left heart back into the pulmonary artery. The neonate with TGA will become profoundly hypoxic and acidotic shortly after birth unless there sufficient shunting of oxygenated pulmonary venous blood into the right heart and aorta. TGA is now predominantly detected before birth but reliable prenatal prediction of the neonatal hemodynamics and risks by conventional fetal echocardiography has remained very challenging. On the other hand, maternal hyper-oxygenation (MH) to increase the fetal O₂ saturation may be used to mimic the drastic events that occur during the normal transition from fetal circulation to the postnatal physiology that includes dilation of the

pulmonary vasculature, increase in pulmonary arterial blood flow and left atrial pre-load, potentially affecting shunting of blood across the atrial septum. In this prospective pilot study we will determine whether MH is a useful diagnostic test to separate fetuses with insufficient intracardiac shunting from those with adequate shunting early after delivery.

2. BACKGROUND & STUDY RATIONALE

2.1 Clinical relevance of TGA

TGA is the predominant cardiac cause of neonatal cyanosis and affects 5-7% of newborns with congenital heart disease (1). The condition is usually repairable with a neonatal ASO, which carries a low surgical mortality risk of 2-5% (2, 3). Indeed, morbidity and mortality is nowadays greater in the preoperative period. Many preoperative problems are secondary to a restrictive or intact atrial septal (RAS) communication, and/or ductal constriction, resulting in inadequate shunting of oxygenated blood to the right heart, systemic hypoxemia and rapid progression to acidosis, neurological injury and shock (4-7, 9). Yet even with an in-utero patent atrial septum, a newborn may become critically ill shortly after birth once the FO closes. Immediate neonatal balloon atrial septostomy (BAS) becomes a life-saving procedure in this situation. Of neonatal survivors, persistent pulmonary hypertension of newborn (PPHN) is another possible association with a poor postnatal outcome, affecting ~1-3% of children with TGA (6, 8).

2.2 Prenatal Cardiac Imaging

Most cases of TGA in Ontario are nowadays detected before birth and referred to the Fetal Cardiac Program at the Hospital for Sick Children. All patients undergo repeated assessment before birth including a final fetal echocardiogram and a fetal MRI before delivery for prediction of the neonatal risk of severe cyanosis. This is standard care and not research-related.

Better prediction of the neonatal hemodynamics before birth would dramatically facilitate the perinatal care of babies with TGA but is not reliably obtained by conventional imaging.

The prenatal risk assessment of TGA is currently based on the two-dimensional and Doppler echocardiographic evaluation of the heart and in particular of possible shunts across the atrial septum, the ventricular septum, and the arterial duct. In the fetal circulation, the foramen ovale (FO) is an important provider of oxygenated umbilical blood from the placenta to the left heart. The crescent shaped FO, located in the central portion of the secundum atrial septum, progressively increases in width up to 6 mm at term. The thin, mobile septum primum is positioned on the left side of the atrial septum and functions as a flap valve of the FO. During most of the cardiac cycle, it is pushed into the left atrium (LA) by the steady stream of blood that enters the FO. The fetal echocardiographic evaluation of the atrial septum mainly relies on the size of the FO, the position, mobility and shape of the FO flap and the documentation of right-left shunting across the foramen ovale. The prenatal evaluation of the arterial duct includes the echocardiographic assessment of its diameter and documentation of ductal patency and flow direction by color and pulse wave Doppler imaging.

Fetal MRI offers a versatile set of additional tools to assess the fetal physiology and is routinely offered to parents at SickKids to examine the hemodynamic alterations of cardiac lesions and the

impact on the perfusion of organs such as the brain (6–8). Our center has significant experience with the clinical-research applications of MRI in the human fetus (9). This includes the application of fetal MRI in combination with MH (REB No 1000048468).

Importantly, MRI and echocardiographic imaging pose no known risks to the fetus and the mother.

2.3 Maternal Hyperoxygenation

This study will examine whether MH is useful as a diagnostic test to more accurately detect TGA patients with poor vs. good neonatal intra-cardiac mixing of blood, based on the in-utero response to oxygen exposure. Acute maternal oxygen administration will transiently increase the fetal oxygen levels to those reached at birth with spontaneous breathing, thus simulating conditions that will naturally occur at the time of birth. Echocardiogram and MRI will be used to examine the effects on the fetal circulation. This is the research-component of this study.

It has been discovered 80 years ago that maternal inhalation of oxygen during labour increases the oxygen content in the umbilical cord. In the sheep model, e.g., maternal administration of 100% oxygen increases the fetal arterial pO₂ from 20-25 mmHg to ~30-35 mmHg and the arterial O₂ saturation from 65% to 80%. Similarly, MH increased the UV O₂ saturation from 75% to 95% and UV pO₂ from 32-35 mmHg to 40-50 mmHg (10).

The effects of MH were also studied in the human fetus. Brief maternal administration of 65-70% O₂ via a face mask during the last trimester, *which is what will be used in our study*, led to a significant increase in UV O₂ saturation in the normal fetus followed by pulmonary vasodilatation. If maternal O₂ was administered over a prolonged period in late gestation, the effect on the pulmonary vasculature disappeared within a few hours.

Limited information is available about the most appropriate amount of O₂ to be used for MH. Experimental data from animal and human subjects showed that increasing FiO₂ from room air to 40% resulted in the greatest increase in fetal PaO₂, and maximal effects on the fetal circulation. Furthermore, inhaled O₂ up to 15L/min is well tolerated via a simple face mask, which results in a FiO₂ of ~40 to 50%. While no adverse effects of chronic MH were reported when used to treat fetal growth restriction (14-16), a Cochrane review (11) of experimental animal data raised the possibility that chronic maternal hyperoxygenation could reduce uterine arterial blood flow, and thus recommended further investigations if chronic maternal O₂ was to be used for this indication. *This is not expected with acute hyperoxygenation. Effects on the arterial duct are also unlikely to occur due to the short duration of O₂ supplementation: it usually takes at least 1-2 days for spontaneous ductal closure at birth. Ductal constriction was not observed in any of the previous studies using MH (12).*

In this study, we will examine the added diagnostic value of acute MH in predicting neonatal maladaptation due to poor intracardiac mixing of oxygenated blood. MH (70% of O₂ by face mask) will be administered in late gestation at two separate occasions, during echocardiography and MRI. The rate and duration of MH (10 to 15L/min by mask for up to 30-45 minutes/test) is considered to be safe to the mother and her fetus. We know that if acute MH is used in the normal 3rd trimester fetus with a patent FO, this leads to pulmonary vasodilation, a 30-50% increase in pulmonary blood flow and in left atrial load, as well as a reduction in DA flow by

fetal MRI (13). Data on the acute effects of MH on fetal TGA are limited and no specific studies have been performed to study the response of the pulmonary vasculature to supplementary O₂. MRI data obtained without the use of MH in 4 fetuses with TGA/IVS and suspected RAS at SickKids (14) demonstrated significantly reduced flow across the FO, increased combined cardiac output, and increased flow in the ascending (AAo) and descending (DAo) aorta, UV, and aorto-pulmonary collaterals when compared with normal fetuses. The fetus with the lowest FO shunting and highest aorto-pulmonary collateral flow died from PPHN after birth.

2.4 Study Rationale

To examine the baseline fetal hemodynamics as well as the response to acute MH as an added diagnostic test, we will combine various fetal echocardiographic and MR imaging tools. The prenatal findings will then be compared to the neonatal presentation.

We postulate that conditions that predispose newborns to acute neonatal compromise will be detectable and distinguishable prior to birth by echocardiography, MRI, or by combining the findings of both exams. We expect to encounter the following 4 clinical scenarios:

- 1) *TGA/IVS with unrestricted atrial shunting before and after birth:* we expect fetal baseline differences in LV/RV O₂ content and DAo/AAo O₂ content related to unrestricted right-left atrial shunting. MH is expected to further increase the differences in LV/RV O₂ content and DAo/AAo O₂ content, which leads to an increase pulmonary blood flow, LV preload and LV stroke volume due to O₂-mediated vasodilation of the pulmonary vasculature. As a confirmation of pulmonary vaso-reactivity to O₂, the branch PA pulsatility index will decrease by $\geq 10\%$ and this will coincide with lower peak systolic flow and reversal of end-diastolic flow across the DA.
- 2) *TGA/IVS with in-utero RAS:* In the absence of intracardiac shunting, RV/LV and DAo/AAo O₂ content will be equal at baseline and with MH and no significant effect on pulmonary flow will be observed.
- 3) *TGA/IVS with postnatal RAS:* RV/LV and DAo/AAo O₂ content will differ at baseline when the FO is still patent. With MH-induced functional closure of the FO by the septal flap, the RV load and AAo O₂ content will preferentially increase to reach an equal or higher oxygen content and saturation when compared with the LV, MPA, DA and DAo.
- 4) *TGA with PPHN:* supplementary maternal O₂ will not affect fetal pulmonary blood flow and PA pulsatility.

2.5 Potential Benefits and Risks of Study Participation

The potential implications of this study are clinically important. Not only would it help with the parental counselling and facilitate the perinatal care of future fetuses with TGA but for TGA/IVS with severe RAS it may also offer the possibility of a pre-delivery BAS or a planned delivery with ECMO stand-by to prevent hypoxic organ damage (18).

The risk to the mother will be the potential of some discomfort related to the oxygen administration and the added time of the exams. We may also detect findings that have not been detected previously by echocardiography, which will then have to be disclosed to the family and may cause additional parental concerns.

3. COMPLIANCE STATEMENT

This study will be conducted in full accordance with all applicable Hospital for Sick Children research policies and procedures, International Conference on Harmonisation Good Clinical Practice (ICH GCP) and all applicable regulations and the PHIPA Privacy Rule. Any episode of noncompliance will be documented.

The investigators will perform the study in accordance with this protocol, will obtain consent, and will report unanticipated problems in accordance with Hospital for Sick Children REB policies and procedures and applicable regulatory requirements. Collection, recording, and reporting of data will be accurate and will ensure the privacy, health, and welfare of research subjects during and after the study. The protocol, informed consent form(s), recruitment materials, and all participant materials will be submitted to the Research Ethics Board (REB) for review and approval.

4. STUDY OBJECTIVES

The purpose of the study is to detect prenatal findings that are associated with early postnatal morbidity and mortality.

4.1 Primary Objective

The primary objective is to examine and characterize the response, or lack thereof, to acute MH as a diagnostic test on intracardiac/ductal shunting and pulmonary blood flow among fetuses with TGA, and to clarify its associations with measures of neonatal outcomes.

4.2. Secondary Objectives

A secondary objective will focus on the acute effects of MH on the cerebral perfusion.

4.3 Study Endpoints

Study endpoints are any of the following outcomes: survival to discharge from Hospital as a primary outcome. A secondary outcome will be any evidence of perinatal compromise as defined in the protocol. This will be associated with the fetal response to oxygen. For cases with PPHT with RV pressure $>50\%$ of the systemic pressure at the time of discharge, the outcome to 1 year of life will be ascertained.

5. INVESTIGATIONAL PLAN

5.1 Study Design

This is a prospective single centre study on the association between prenatal cardiovascular findings, the fetal response to MH and neonatal morbidity and mortality.

5.2 Patient Numbers and Study Duration

Recruitment will be from the time of REB approval of this study to the time 50 patients have successfully completed the study. We follow approximately 30 women per year with a fetal

diagnosis of simple TGA, defined as TGA either with an intact ventricular septum or with ventricular septal defect(s) (VSD). The rate of pregnancy termination is low (<5%) as most affected babies do not carry a risk of significant non-cardiac disorders. Parents of a child with congenital heart disease are also highly motivated in participating in research that might help their or other children with the same condition and we anticipate that at least 80% of eligible women will be willing to participate in this research. Based on these assumptions, we anticipate being able to successfully recruit 50 participants within ≤ 2.5 years.

5.3 Eligibility Criteria

Inclusion Criteria:

- 1) Pregnant mothers ≥ 18 years of age
- 2) Fetal diagnosis of simple TGA and intention of active treatment after birth
- 3) Written maternal informed consent

Exclusion criteria:

- 1) Termination of pregnancy
- 2) Complex TGA (e.g. Taussig-Bing anomaly or moderate-severe outflow tract obstruction, fetal arrhythmia such as frequent premature atrial beats, abnormal baseline heart rate (<110 bpm; > 160 bpm) in the third trimester)
- 3) Major non-cardiac lesions
- 4) Significant maternal co-morbidities that precludes a fetal MRI (e.g. significant obesity, claustrophobia)

6. STUDY PROCEDURES

6.1 Study Procedures

Antenatal diagnosis of TGA followed by a referral to the Fetal Cardiac Program at SickKids is typically made during mid-gestation. Fetal echocardiography including a late-gestational MRI is routinely used in the assessment of all prenatally diagnosed TGA.

The initial echocardiogram allows differentiating between simple vs complex form of TGA and determining whether or not a patient fulfills eligibility criteria to potentially participate in the study. The physician will explain the possibility of MH in the last trimester that as a diagnostic test may help with the management of future patients with the same condition. If the patient is interested in hearing more details about MH, more information will be provided to help families decide whether they would like to participate in the study. This will allow coordination of echocardiograms and MRI studies on the same day, whenever possible.

Mothers with fetal TGA are routinely seen at SickKids for a final fetal echocardiogram in late gestation (≥ 34 gestational weeks). The final exam includes detailed re-evaluation of all cardiac structures including blood flows across the atrial septum, AV and semilunar valves, arterial duct, pulmonary and cerebral blood flows, among other. Following the exam, perinatal management recommendations are made and discussed with the family. This typically includes the

recommendation of 1) delivery at Mount Sinai Hospital, 2) initiation of IV prostaglandin at birth, and 3) referral to SickKids critical cardiac care unit for early neonatal care that may include preoperative BAS. Whether a mother elects to participate or not in this study, the baseline echocardiogram and perinatal management will not be affected by the maternal decision.

The following are study-related additional procedures, if a mother who fulfills all inclusion and none of the exclusion criteria consents in writing to participate in this study:

- 1) A fetal echocardiogram during acute MH
- 2) A fetal MRI during acute MH

6.1.1 Consent Process

The study may be explained by the fetal cardiology team prior to the last prenatal encounter. Maternal consent will be obtained by a person (research coordinator or another physician) who has no direct involvement in the care of this patient at the second last (generally 28-30 weeks) visit or at the time of the last fetal exam (≥ 34 weeks). Moreover, it will be explained that she can drop out of the study at any time. Once enrolled, participants (mother and child) will be assigned individual study numbers to allow de-identified data entry in a password protected Excel database that will be securely stored on the SickKids server and be accessible to the research team only.

6.1.2 Fetal Echocardiography

All fetal echocardiograms will be performed with standard GE Voluson E-10 or Philips IU 22 ultrasound systems within the Echo Lab facility or the Cardiac Diagnostics & Interventions Unit (CDIU) at SickKids. Fetal echocardiography poses no known risks to the mother and her fetus.

At the final visit, the mother will initially undergo a baseline fetal echocardiogram that will include the assessment of left and right ventricular outflow tract (peak flow, velocity time integral (VTI), heart rate, aortic and pulmonary valve diameters), the arterial duct (systolic and end-diastolic flow, forward/reverse flow ratio, VTI, diameter), branch pulmonary artery (peak flow, pulsatility index calculated as peak systolic velocity – end-diastolic velocity/mean velocity), pulmonary veins (VTI), atrial septum (FO diameter, atrial shunt direction and velocities, atrial septal excursion), mid cerebral artery (peak, VTI), as well as ventricular dimensions (diameter in 4CV; volumes by 3/4D). These findings will be digitally recorded and all measurements will be made offline by the responsible cardiologist to abbreviate the duration of the exam. The percent changes in flow VTIs, percent changes in flow PIs and DA forward/reverse flow ratios will be calculated using the echocardiography data.

Immediately following the baseline echocardiogram, maternal oxygen will be administered in the same room via a sterile face mask to reach about 65-70% of oxygen and delivered at a rate of 10 to 15L/minute. After a 5 minute-period to allow fetal steady-state oxygenation, the same echocardiographic variables as above will be recorded during continuous maternal O₂ supplementation, which is expected to take maximally 30 minutes or less. During the exam, the fetal wellbeing will be continuously monitored by fetal echocardiography, which allows us to continuously see the baby's movements and heart function. Oxygen supplementation will be

stopped once the above imaging variables have been obtained or after a maximum of 30 minutes (5 minutes initiation + 25 minutes echocardiogram) if the test cannot be completed within this time frame. No further research related measurements will be obtained once the MH has terminated.

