6.1.3 Fetal MRI

We routinely perform late-gestational MRI for fetal TGA before birth to examine fetal hemodynamics and the brain. Fetal MRI poses no known risks to the mother and her fetus. Baseline and MH MRI will be performed as usual with a clinical 1.5T MR system in the CDIU. No sedation or invasive techniques will be required to perform MRIs on pregnant women. The MRI study will take a maximum of 90 minutes including MH study, which is expected to take maximally 45 minutes. The subjects will be fitted with their usual supply of oxygen via a face mask during MRI. The same amount of O₂ at the same flow rate will be administered as described above.

As with all our fetal MRI studies, a standard multichannel body surface coil will be placed over the maternal abdomen and imaging performed for a maximum of one hour. MR flow assessments will be acquired according to our previously published technique to examine the distribution of blood flow across the fetal circulation (15). The PC MR acquisitions will be analyzed using a commercial software (Q-flow, Medis) and the oximetry measurements will be analyzed using a region of interest placed over the central 50% of the vessel diameter on the T2 map, according to our previously published techniques (15,16). The imaging protocol has been detailed in previous publications and includes T1 and T2 weighted imaging, diffusion tensor imaging, MR spectroscopy and brain volumetry (15,17). MR oximetry will be recorded in the ascending aorta (AAo), superior vena cava (SVC), descending thoracic aorta (DAo), umbilical vein (UV) and main pulmonary artery (PA). Oxygen content at baseline and during MH will be measured offline at the level of the LV/MPA, RV/AAo and DAo. Blood flow quantifications (baseline and MH; cine-phase contrast) will be made in the AAo, DAo, main and branch PAs, SVC, IVC, UV and DA. Other variables will include estimated hematocrit (HCT), fluximetry, brain volumetry (baseline; 3D steady state), cDO₂ and cVO₂ (baseline and MH; T2 mapping) to measure oxygen consumption. Oxygen supplementation will be stopped once the above imaging variables have been obtained or after a maximum of 45 minutes (5 minutes initiation + 40 minutes MRI) if the test cannot be completed within this time frame. No further research related measurements will be obtained once the MH has terminated.

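### The protocol does not mask the reader to oxygen condition, so expectation bias of unknown size can enter the measured within-fetus response to MH

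*Combined protocol and SAP*

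**What the plan says.** Section 6.1.2 sets a fixed order. "Immediately following the baseline echocardiogram, maternal oxygen will be administered in the same room via a sterile face mask", and after a five-minute lead-in "the same echocardiographic variables as above will be recorded during continuous maternal O₂ supplementation". The recordings are stored, and "all measurements will be made offline by the responsible cardiologist to abbreviate the duration of the exam". The stated purpose of offline reading is a shorter exam; masking is not mentioned. The response measures are then derived from these paired readings: "The percent changes in flow VTIs, percent changes in flow PIs and DA forward/reverse flow ratios will be calculated using the echocardiography data".

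Section 2.4 records what the investigators expect. With unrestricted atrial shunting, "As a confirmation of pulmonary vaso-reactivity to O₂, the branch PA pulsatility index will decrease by" at least 10%, together with changes in ductal flow. With pulmonary hypertension of the newborn, "supplementary maternal O₂ will not affect fetal pulmonary blood flow and PA pulsatility". With an atrial septum already restrictive in utero, no significant effect on pulmonary flow is expected.

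For MRI, section 6.1.3 says "Oxygen content at baseline and during MH will be measured offline". It names no reader. It fixes the oximetry region of interest at the central 50% of the vessel diameter and has flow analysed in commercial software.

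No section describes removal of the oxygen label, random ordering of loops, a second reader or a repeatability check.

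**The concern.** The primary objective in section 4.1 begins with characterising the response to MH, and the secondary objective in section 4.2 is the acute effect on cerebral perfusion. Both rest on differences between two readings in the same fetus. Doppler measurements, diameters and septal excursion leave room for reader judgement. If a reader who knows the condition leans even slightly toward the expected answer, the lean goes straight into the difference.

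More patients would not remove it. The Bland-Altman plot planned in section 8 would show it as part of the mean change and could not separate it from a true oxygen effect. This exposure is distinct from knowledge of the neonatal outcome: it would exist even if every reading were finished before birth.

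**Working it through.** **1. The plan's own figure.** The only number that bears on size is the PI fall of at least 10% in section 2.4. It comes with no derivation, no standard deviation of PI change and no intra- or inter-reader repeatability, so it cannot be reproduced. Everything below is conditional on assumed values.

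**2. What kind of reading error matters.** Read in the usual way, the PI in section 6.1.2 is (S - D)/M, where S is peak systolic, D end-diastolic and M mean velocity. If a reader over- or under-traces all velocities by a common factor k, then (kS - kD)/(kM) = (S - D)/M and the PI does not move. Bias in the PI needs selective error in one of its terms. The next step therefore assumes shading of the PI itself. VTIs are not protected by this cancellation.

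**3. Apparent change with no true effect.** Let the baseline PI be read high by a fraction d and the oxygen PI low by d. The apparent change is (1 - d)/(1 + d) - 1.

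| Assumed d | Calculation | Apparent change |
|---|---|---|
| 2% | 0.98/1.02 - 1 | -3.9% |
| 3% | 0.97/1.03 - 1 | -5.8% |
| 5% | 0.95/1.05 - 1 | -9.5% |

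To reach -10%, (1 - d)/(1 + d) = 0.90, so d = 0.10/1.90 = 5.3% on each reading.

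**4. Effect if someone counted falls of 10% or more.** Section 8 does not plan this count, so it is illustration only. For a fetus with no true change, the chance of reading a fall of at least 10% is Φ((bias - 10)/SD), in percentage points.

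| Assumed SD of PI change | No bias | 5-point bias |
|---|---|---|
| 5 | 2.3% | 15.9% |
| 10 | 15.9% | 30.9% |
| 15 | 25.2% | 36.9% |

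**5. Effect on the ROC analysis.** A bias that multiplies or shifts every fetus's response equally preserves rank order, so the area under the curve (AUC) is unchanged. Suppose instead that the bias differs by δ points on average between outcome groups with no true difference. Under a binormal model, AUC = Φ(δ/(SD√2)), against 0.50 without bias.

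| Assumed SD | δ = 5 | δ = 10 |
|---|---|---|
| 10 | 0.64 | 0.76 |
| 15 | 0.59 | 0.68 |
| 20 | 0.57 | 0.64 |

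A route to such a difference exists. Section 6.1.2 has the same reader measure the atrial septum at baseline, and section 2.4 ties the expected response to septal anatomy. Section 2.2 says conventional imaging does not reliably predict neonatal hemodynamics, so a lean based on septal appearance would translate only partly into a difference between outcome groups.

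**The case against.** The case against giving this much weight has several good parts.

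- **Knowledge of condition.** A reader might infer that the cardiologist knows which loops were taken on oxygen. The text does not say so. It is silent on masking, and the word responsible only suggests someone familiar with the case. What stands is that no masking is provided for.
- **Size.** A reader might infer a bias about as large as the 10% fall. That is the top of an assumed range, and proportional velocity errors cancel in the PI. The documents support no size.
- **Role of the 10%.** It is an expected finding in one scenario of section 2.4. Section 8 sets no responder cut-off, so no planned analysis turns on crossing it.
- **Direction.** Section 2.4 lists four scenarios and some predict no pulmonary effect, so there is no single direction to lean toward. This is true, but it cuts both ways: expectations that differ by anatomy are what could make the bias differ between fetuses and reach the AUC.
- **Diagnostic result.** A reader might infer that the ROC analysis is invalid. Under a common bias it is untouched.
- **MRI.** The reader is unnamed and oximetry follows a fixed region rule, so that part is less exposed, although someone still places the region. Much of the cerebral perfusion objective rests on MRI; the echo share is the middle cerebral artery Doppler.
- **Study type.** Section 8 calls this a small feasibility and safety study with descriptive statistics. That lowers the stakes, but the same section uses the data to describe ranges of response and to test diagnostic value.

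Nor would an added control condition be the answer: read unmasked, it would carry the same problem.

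**Conclusion.** The gap is real and worth closing before research measurements begin. Fixed acquisition order, offline reading with no masking provision, and expectations written in advance together leave the measured response to MH open to expectation bias. Its size is unknown. The -4% to -10% range holds only if the PI itself is shaded by 2% to 5% in opposite directions on the two readings, which is an assumption and not an estimate.

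The mean response is the quantity chiefly at risk, with the echo part of the cerebral perfusion objective alongside it. The AUC is at risk only if the bias differs between fetuses, and the AUC figures above also assume a normal model with chosen SDs. The documents do not show that the reader is unmasked in practice, that the bias approaches 10%, or that the diagnostic analysis fails.

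**What to change.** Add to section 6.1.2 that, for the research measurements, stored echo loops are exported without oxygen label or time stamp, coded, and presented in random order, and that the measurements are saved before the code is broken. Apply the same to the MRI series in section 6.1.3 where feasible. The same cardiologist or MRI reader can do this, since reading is already offline. Clinical reading of the baseline exam stays as it is.

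The cost is some file handling per case. Section 6.1 makes the final echo a clinical exam that guides perinatal recommendations, so baseline loops already read for care may need to be measured again for research. Masking may be incomplete where the oxygen effect is visible on the image, such as reversed end-diastolic ductal flow. No extra imaging, oxygen exposure or participants are needed, and no sample size figure changes, because the plan has no power calculation.
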